4.2. Protocol Deviations

Protocol deviations will be classified into major or minor deviations by medical review. A major deviation is defined as a deviation that may significantly impact the completeness, accuracy and/or reliability of the trial data; that may significantly affect a patient's rights, safety and well-being (ICH.E3 R1 Structure and Contents of Clinical Study Reports Guidance for Industry. 2013). Deviations not classified as major will be assigned as minor. Major protocol deviations

will be reviewed and approved by Alnylam prior to an interim or full database lock. All protocol deviations will be presented in a listing.

Major protocol deviations will be summarized in the CSR.

5. GENERAL STATISTICAL METHODS

5.1. Sample Size Justification

The planned enrollment for the study is 20 patients, including at least 6 patients in each cohort.

Of those 20 patients, the planned enrollment includes at least 4 patients <6 years of age at consent, and at least 2 patients between ≥ 6 to <18 years of age at consent.

The sample size was determined based on feasibility considerations, not power calculations.

5.2. General Methods

Continuous data will be described using descriptive statistics such as the number of observations (n), mean, standard deviation, standard error, median, quartiles, minimum, and maximum. For the summary statistics of all numerical variables unless otherwise specified, minimum and maximum will be displayed to the same level of precision as reported. Median and mean will be presented to the level of precision collected in the database plus one additional decimal. The standard deviation and standard error will be presented to the level of precision collected in the database plus 1 additional decimal. For any assessments with repeated collections at a given study visit (eg height) the mean will represent the value at that visit unless otherwise noted. For biomarker and/or lab data, if any value is recorded as <lower limit of detection (LLOD) then the value assigned for calculations will be the LLOD.

Categorical and ordinal data will be described using the patient count and percentages in each category. When count data are presented, the percentage will not be presented when the count is zero.

Summaries of tables and figures for each study period will include all data collected during the corresponding period as defined in Section 4.1.

The per-patient listings will include all data collected during each study period. For per-patient listings of the extension periods, there will be a variable to indicate the period of the data collection (Primary Analysis Period or Extension Period).

Day 1 will be defined as the day of the first dose of lumasiran. Study day is calculated relative to the first dose date of lumasiran for all patients:

If the assessment date is after the date of first lumasiran dose, then the study day will be calculated as:

$$\text{Study Day} = \text{Date of assessment} - \text{date of first dose of lumasiran} + 1,$$

If the assessment date is before the date of the first dose of lumasiran, then the study day will be calculated as:

$$\text{Study Day} = \text{Date of assessment} - \text{date of first dose of lumasiran}$$

Summary statistics will be presented, as well as 2-sided 95% confidence interval (CI)s for primary/secondary endpoints or selected parameters, as described in the sections below.

All data recorded on the CRF will be displayed in data listings.

5.3. Computing Environment

All statistical analyses will be performed using validated SAS statistical software Version 9.4 (or later), unless otherwise noted.

5.4. Baseline Definitions

In Cohort A patients, the plasma oxalate baseline is defined as the mean of all plasma oxalate level values collected prior to the first dose of lumasiran. In Cohort B patients, the plasma oxalate baseline is similarly defined except that the values obtained from the plasma oxalate profile assessment visits will only include the first pre-dialysis sample collected per visit.

For all patients who are not anuric (anuria is defined as <100 ml of urine per day), single-void urine samples (in triplicate) will be collected during screening, with the mean of values for the various parameters measured in these single-void samples used to establish baseline. In these patients, three 24-hour collections will be performed during Screening, with the median values of all the valid samples used to establish baseline urinary oxalate levels.

A 24-hour urine collection will be considered valid if each of the following criteria are met:

- The collection is between 18 to 26 hours in duration between the initial discarded void and the last void or attempt to void.
- No voids are missed between the start and end time of the collection.
- In patients not undergoing dialysis, the 24-hour creatinine content is at least 5 mg/kg for patients <6 years of age, and 10 mg/kg for patients ≥6 years of age as measured in the study central laboratory.

In patients undergoing dialysis, 24-hour collections are not required to have a minimum creatinine content to be considered valid.

Urine data collected from patients that are anuric is considered unreliable; thus there will be no analyses performed for patients that were anuric, from whom urine samples are not collected.

In Cohort B, baseline plasma oxalate AUC measurements will be obtained via the plasma oxalate profile assessments prior to the first dose of lumasiran. Plasma oxalate profile assessments will be performed during Screening, with the mean value of all valid AUC profiles (see Section 7.3.1) being computed to establish the baseline AUC.

For other parameters, baseline is defined as the last non-missing value prior to the first dose date/time of lumasiran, unless otherwise specified. The baseline value for any measurements with multiple values at a visit (eg labs, etc.) will be defined as the mean of all values collected on the most recent date of assessment prior to the first dose date/time of lumasiran.

Parameters capturing disease history (eg reported history of renal stone episodes in the past 12 months) at screening will represent the baseline value (adjusted events based on age category will be applied, see Section 10.1).

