6.2.2. Urinary Oxalate

In patients in both Cohort A and Cohort B who are not anuric (ie, patients who are able to continue to produce urine ≥ 100 ml per day) and are able to complete the collection procedure, 24-hour urinary oxalate excretion will be assessed. Since not all patients will be able to provide 24-hour urine samples, single-void urine samples (in triplicate) will be collected throughout the study in all patients who are not anuric. Table 12 shows the 24-hour urine collection procedure by study visit.

In patients who are able to comply with 24-hour urine collection procedures, urinary oxalate excretion will be determined from 24-hour urine sample collections to be completed at the time points specified in the Schedules of Assessment (see Table 1, Table 2, Table 3, and Table 4). Urinary oxalate concentrations will be analyzed centrally using a validated assay. 24-hour urine collections in patients not undergoing dialysis must meet pre-specified validity criteria (see Section 6.2.2.1).

For patients who are able to comply with the 24-hour urine collection procedure, three 24-hour urine collections will be scheduled during screening to establish baseline urinary oxalate excretion. For Month 6, three 24-hour urine collections will be scheduled within 14 days prior to dose to evaluate changes in oxalate concentrations over the 6-month interval. A single 24-hour collection will be scheduled at Month 3, Month 12, and then every 6 months thereafter as specified in the Schedules of Assessments (see Table 1, Table 2, Table 3, and Table 4). In patients undergoing dialysis, the timing of the collections relative to patients' weekly dialysis schedule should remain consistent for each patient, when possible.

Patients able to comply with 24-hour urine collections will either bring a 24-hour urine collection to the clinic, courier samples to the laboratory, or have their 24-hour urine collected during an inpatient stay at the time of the study visit.

All patients who are not anuric will have 3 single-void urine samples collected during Screening (first morning voids are preferred, when feasible). Following screening, single-void collections are performed within 7 days predose, as specified in the Schedules of Assessment (see Table 1, Table 2, Table 3, and Table 4). Samples may be collected as an outpatient prior to the visit or collected during the study visit prior to dosing, as applicable.

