AUC(0-24h) will be calculated using plasma oxalate results with the linear-trapezoidal method using actual collection times relative to pre-dialysis sampling time. An exact 24h assessment for the purpose of calculating the AUC(0-24h) will be calculated using linear interpolation or extrapolation on the two non-missing scheduled assessments closest to the 24-hour timepoint.

Plasma oxalate profiles will be compared across visits within patients. LS mean percent change from baseline plasma oxalate AUC(0-24h) at Month 6 and its associated 95% confidence interval will be estimated using MMRM model including data evaluated at Month 3 and Month 6. Additionally, the AUC(0-24h) parameter will be listed and descriptively summarized by study visit. The Full Analysis Set will be used for this analysis. A similar approach as used for the primary analysis will apply, in case when the model fails to converge.

Additionally, AUC(4-24h) will be similarly analyzed. AUC(4-24h) is defined as the plasma oxalate area under the curve of the 20 hour window from the end of dialysis (30 minutes before the end of dialysis assessment) until the next dialysis session (24h timepoint). This approach is intended to reduce the variability introduced by different dialysis parameters between patients. The percent change from baseline in plasma oxalate AUC(4-24h) will be summarized through Month 6 in a similar manner to the percent change from baseline in plasma oxalate AUC(0-24h) as a sensitivity analysis to the secondary endpoint. The pre-dialysis scheduled assessment will not be required for a valid AUC or utilized in this assessment, otherwise this analysis will remain consistent with methodology to assess the percent change from baseline in plasma oxalate AUC(0-24h).

7.3.2. Change from baseline to Month 6 in other Plasma and Urinary Oxalate Parameters

The analyses for the following secondary endpoints will also be performed using a restricted maximum likelihood based Mixed-effect Model Repeated Measures approach.

- Absolute change from baseline to Month 6 in plasma oxalate during the Primary Analysis Period
- Percent change and absolute change from baseline to Month 6 in 24-hr urinary oxalate corrected for BSA during the Primary Analysis Period
- Percent change and absolute change in spot urinary oxalate: creatinine ratio during the Primary Analysis Period

[figure not shown]

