Analysis by cohort will include evaluable assessments through Month 6, which will be modeled with fixed effects of scheduled visits and baseline covariate of corresponding assessment,

including patient as a random factor. LS mean of an endpoint of Month 3 to Month 6, averaged over these timepoints will be presented along with corresponding SEMs and 95% CIs. The autoregressive (1) covariance structure matrix will be used to model the within-patient error given the small sample size for this study. Similar approach as used for the primary analysis will apply, in case when the model fails to converge.

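### 24-hour urinary oxalate: baseline is a median, while Month 6 falls to the default mean and Month 3 is a single value, so the reduction may be slightly understated

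*SAP*

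**What the plan says.** - **Baseline (SAP 5.4).** Three 24-hour collections are planned at Screening, "with the median values of all the valid samples used to establish baseline urinary oxalate levels". For single-void urine the same section uses the mean: "with the mean of values for the various parameters measured in these single-void samples used to establish baseline". The plasma oxalate and plasma oxalate AUC baselines are means as well.
- **Repeated collections at a visit (SAP 5.2).** The general rule is that "the mean will represent the value at that visit unless otherwise noted".
- **Number of collections (Protocol 6.2.2).** "For Month 6, three 24-hour urine collections will be scheduled within 14 days prior to dose". Also: "A single 24-hour collection will be scheduled at Month 3, Month 12, and then every 6 months thereafter".
- **Endpoint (SAP 7.3.2).** "Percent change and absolute change from baseline to Month 6 in 24-hr urinary oxalate corrected for BSA during the Primary Analysis Period". The reported estimate is a model-based mean over visits: "LS mean of an endpoint of Month 3 to Month 6, averaged over these timepoints will be presented", with standard errors and 95% confidence intervals.
- **Validity (SAP 5.4).** "The collection is between 18 to 26 hours in duration", with no missed voids. Patients not on dialysis must also meet a minimum creatinine content.

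Neither SAP 5.4 nor SAP 7.3.2 says how the three Month 6 collections are combined. SAP section 8 (changes to planned analyses) gives no reason for using a median here.

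**The concern.** A programmer following the SAP would divide a Month 6 mean by a baseline median. The two statistics estimate different quantities when variation is skewed: for right-skewed values, the mean of three is larger on average than the median of three. Part of the computed change would then come from the choice of summary and not from the drug. Both the percent and the absolute change in 24-hour urinary oxalate are exposed.

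The choice also looks unintended, because every other oxalate baseline in SAP 5.4 is a mean.

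**Working it through.** The SAP quotes no bias or precision for this endpoint, and the sample size rests on feasibility, so there is no stated figure to reproduce.

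**Inputs from the documents.** Three collections at baseline, one at Month 3, three at Month 6. Median at baseline; mean at Month 6 by default. Illustrative reduction of 64%: the mean maximal fall in 24-hour urinary oxalate that Protocol 1.2.2 reports from the Phase 1/2 study, in patients with preserved renal function.

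**Assumptions not in the documents.** Lognormal variation between collections within a patient, with log-SD s = 0.2, 0.3 or 0.5; all three baseline collections valid; true reductions r of 0% and 30% as further cases. The reported LS mean is treated as the simple average percent change.

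**Formula.** Scale baseline to a geometric mean of 1. Let M = E[mean of 3] = exp(s²/2), D = E[1/median of 3] and A = E[1/mean of 3].

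- SAP as written: 100 × [(1 − r) × M × D − 1]
- Mean at both ends: 100 × [(1 − r) × M × A − 1]
- Shift due to the mismatch: 100 × (1 − r) × M × (D − A)

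**Results.** D and A come from simulation.

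| s | M | D | A | Shift, r = 0 | r = 30% | r = 64% |
|---|---|---|---|---|---|---|
| 0.2 | 1.0202 | 1.0089 | 0.9934 | 1.6 | 1.1 | 0.6 |
| 0.3 | 1.0460 | 1.0204 | 0.9860 | 3.6 | 2.5 | 1.3 |
| 0.5 | 1.1331 | 1.0577 | 0.9650 | 10.5 | 7.4 | 3.8 |

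For example, at s = 0.3 and r = 0: 1.0460 × (1.0204 − 0.9860) = 0.036, or 3.6 points. Multiplying by 0.70 gives 2.5, and by 0.36 gives 1.3. Shifts are positive, so the reduction is understated.

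**Month 3.** A single collection has the same expectation M as a mean of three, so dividing it by a baseline median carries the same shift. Averaging Month 3 with Month 6 does not dilute the problem. It also decides between the two possible repairs. At s = 0.3 with no true change and equal weight on the two visits, the average percent change is:

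- SAP as written: +6.7
- median at baseline and Month 6: +5.4
- mean at both: +3.1

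The +3.1 that remains is ordinary ratio bias and is not due to the mismatch.

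**Absolute change.** With no drug effect, mean minus median averages +0.011, +0.026 and +0.075 of the baseline geometric mean at s = 0.2, 0.3 and 0.5. Mean minus mean averages zero.

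**When the shift shrinks or vanishes.**

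- Under symmetric (normal) variation, absolute change does not shift. Percent change moves by only 0.04, 0.19 and 0.49 points at a within-patient CV of 10%, 20% and 30% with a 64% reduction, relative to mean at both ends.
- With one or two valid baseline collections, the median equals the mean and there is no mismatch.

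**One patient can go either way.** Take Month 6 values 0.6, 0.65, 0.9 (mean 0.7167).

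- Baseline 1.5, 1.6, 2.4 has median 1.6 and mean 1.8333. The change is −55.2% against the median and −60.9% against the mean.
- Baseline 1.0, 1.6, 1.7 has median 1.6 and mean 1.4333. The change is −55.2% and −50.0%.

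The understatement is therefore a statement about the average.

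**The case against.** The strongest defence is that no sentence prescribes a mean for the Month 6 24-hour collections. That follows from a general default illustrated with height. A reader might infer an explicit rule for this endpoint; the documents support only the absence of a specific rule plus a default that fills the gap. This corrects the wording but does not remove the problem, because the default is itself a stated rule and nothing notes an exception.

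Second, a reader might infer a certain bias. The documents establish neither right skew nor three valid baseline collections in each patient, and without both the shift is small or absent. This stands, and the conclusion is conditional on it.

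Third, the no-effect figures are the largest, since the shift scales with the fraction of excretion that remains. At the cited 64% it is 0.6 to 3.8 points. That reduction came from patients with preserved renal function and may not carry over to advanced renal disease, so the whole range should be shown.

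Fourth, the consequence is limited. The endpoint is secondary, SAP 7.3.2 specifies standard errors and confidence intervals but no p-value, and only non-anuric patients able to complete collections contribute. Under right skew the error runs against the drug. All of this lowers the severity, but an understated estimate is still not the intended one.

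Finally, a reader might infer that collections of 18 to 26 hours enter unscaled, which would move a single value by 18/24 − 1 = −25% to 26/24 − 1 = +8%. The documents do not show this. SAP 6.2 gives the unit per 24 hours, and normalisation may happen before the data reach the analysis. The same window applies at both visits, so without a systematic difference in duration it would mainly add noise. It is a query only.

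**Conclusion.** The point holds in a conditional form and is minor. Followed literally, the SAP measures the two ends of this secondary endpoint with different summaries and gives no reason. The size depends on lognormal variation, the assumed log-SD and three valid baseline collections. Across log-SD 0.2 to 0.5, the average understatement runs from 0.6 to 3.8 points at a 64% reduction and from 1.6 to 10.5 points with no true change. The documents cannot narrow this range. Nothing here touches the primary plasma oxalate endpoint, whose baseline is a mean, or the single-void urine endpoint, which uses the mean at both ends.

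**What to change.** In SAP 5.4, define the 24-hour urinary oxalate baseline as the mean of the valid screening collections. In SAP 5.4 or 7.3.2, state that the Month 6 value is the mean of its valid collections, judged by the same validity criteria. Keep the median baseline as a sensitivity analysis.

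The mean is the better choice of the two. It matches the Month 6 default, the single-collection visits at Month 3 and in the extension, and the other oxalate baselines. A median at both baseline and Month 6 would leave Month 3 mismatched.

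Separately, ask the sponsor to confirm whether excretion is normalised to 24 hours before analysis, and to record the answer.

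The cost is one or two sentences in the SAP and one extra sensitivity run. No new data are needed.

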5.5. Missing Data

Patients who discontinue the study treatment prior to Month 6 will be encouraged to remain on study and complete their remaining clinical visits (excluding PK assessments) through the visit at

Month 6 and only safety follow-up visits afterwards. All data collected regardless of whether it was collected before or after treatment discontinuation will be used for efficacy analysis. However, it is possible that data will remain missing.

Plasma oxalate AUC(0-24h) is considered missing if a plasma sample from any of the four, key collection timepoints (ie, pre-dialysis, 30 minutes before the end of dialysis, 4 hours postdose, and 24 hours post dialysis) is missing. Linear interpolation or extrapolation may be applied to determine the availability of values for these timepoints, if appropriate. For calculation of an AUC for plasma oxalate profile, details are provided in Section 7.3.

For safety analyses, no date will be assigned to any AEs with fully missing dates or partially missing dates. An AE will be considered treatment emergent unless it can be unequivocally determined (from the partial onset date and/or a partial or complete stop date) that the event occurred prior to the first dose of lumasiran.

For medications with partial start or stop dates: the first day/month will be imputed for start date, and the last day/month will be imputed for stop date. For medications with a completely missing start date, the medications will be considered as started prior to the first dose of study drug in this study; medications will be classified as prior or both prior and concomitant depending on the medication stop dates. If any medications have a completely missing stop date, then the medication will be assumed as ongoing.

For partial dates of renal stone events (start and stop dates): the first day/month will be imputed for start date, and the last day/month will be imputed for stop date. It is not expected that renal stone dates will be completely missing.

Due to blood sample volume limitations related to patient age/size, missing data in blood sample tests are expected.

The following are considerations for the evaluability of plasma oxalate due to potential post-dose dialysis treatments in Cohort A.

- If a Cohort A patient has at least one plasma oxalate value during Months 3-6 with intervening transient dialysis (<=2 weeks), then the patient's plasma oxalate values that are prior to dialysis and at least 48 hours after the end of the last dialysis session are evaluable and will be included in primary analysis.
- If a patient has at least one plasma oxalate value during Months 3-6 before long-term (>2 weeks) dialysis, then:
 - The patient's plasma oxalate values before the start of dialysis are evaluable and will be included in the primary analysis
 - The patient's plasma oxalate values after the dialysis are unevaluable and will be excluded from the primary analysis
- If a Cohort A patient begins long-term (>2 weeks) dialysis between baseline and Month 3, then the patient's plasma oxalate values post dialysis are unevaluable. Hence, the patient will be excluded from primary analysis for Cohort A and only included in sensitivity analysis

- If a Cohort A patient begins transient (≤ 2 weeks) dialysis between baseline and Month 3, then:
 - Data collected during the patient's dialysis and recovery period (48 hours) are unevaluable and will be set as missing and be excluded from the primary analysis
 - The remainder of the patient's data including baseline to Month 6 are evaluable and will be used in the primary analysis

The following are considerations for the evaluability of plasma oxalate due to potential dialysis modification (clinically significant change in dialysis prescription as assessed by investigator, e.g., frequency or access modality such as catheter to AV fistula) in Cohort B.

- If a Cohort B patient's dialysis is modified for at least 4 weeks after the Month 3 assessment, plasma oxalate collected before dialysis modification are evaluable and will be included in the primary analysis. Data collected after the dialysis modification will be censored.
- If a Cohort B patient's dialysis is modified for at least 4 weeks prior to the Month 3 assessment, patient data after modification of dialysis are considered unevaluable. Hence, the patient will not be included in primary analysis, but will be included in safety analysis set for the sensitivity analysis.
- If a Cohort B patient's dialysis regimen is modified for less than 4 weeks (from the start of the change to the resumption of the prior dialysis regimen), plasma oxalate values during this modification or within 48 hours following the resumption of the prior dialysis regimen are considered unevaluable and will not be included in the primary analysis.

Data collected after an organ transplant or protocol prohibited treatment may be censored for analysis.

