6.3.2. Renal Stone Events

A renal stone event is defined as an event which includes at least one of the following:

- Visit to healthcare provider (eg, outpatient clinic, urgent care, emergency department, procedure) because of a renal stone
- Medication for renal colic
- Stone passage
- Macroscopic hematuria due to a renal stone

All relevant clinical information pertaining to the event should be obtained, including laboratory values, medical records, discharge summaries, and medical test results.

Since renal stone events are recorded as an efficacy assessment for lumasiran, these will not be treated as AEs or SAEs. However, if a patient experiences other AEs or SAEs during a renal stone event, they should be reported (see Section 6.5.6.1).

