3.2. Secondary Endpoints

The following are the secondary endpoints in the Primary Analysis Period:

Primary Analysis Period (Baseline to 6 months)

- Percent change in plasma oxalate AUC between dialysis sessions (Cohort B)
- Absolute change in plasma oxalate
- Change in the following parameters:
 - Urinary oxalate, which is measured by percent and absolute change in 24-hour urinary oxalate excretion corrected for BSA and spot urinary oxalate:creatinine ratio, when available.
 - QoL assessed by the PedsQL Total Score for patients ≥ 2 to < 18 years of age at consent, and as assessed by KDQOL Burden of Kidney Disease and Effect of Kidney Disease on Daily Life subscales, and SF-12 Physical Component Summary and Mental Component Summary, in patients ≥ 18 years at consent
- Plasma PK parameters of lumasiran

The following are the secondary endpoints in the Long-term Extension Period:

Long-term Extension Period (6 months to end of study)

- Percent change in plasma oxalate AUC between dialysis sessions (Cohort B)
- Percent and absolute change in plasma oxalate
- Change in the following parameters:
 - Nephrocalcinosis as assessed by renal ultrasound
 - Frequency and mode of dialysis (Cohort B)
 - Frequency of renal stone events
 - Urinary oxalate, measured by 24-hour urinary oxalate excretion corrected for BSA, and spot urinary oxalate:creatinine ratio
 - Renal function as assessed by eGFR (Cohort A)
 - Measures of systemic oxalosis in the following systems:
 - Cardiac

- Dermatologic
- Skeletal
- Ocular
- QoL (quality of life) assessed by the PedsQL Total Score for patients ≥ 2 to < 18 years of age at consent, and as assessed by KDQOL Burden of Kidney Disease and Effect of Kidney Disease on Daily Life subscales, and SF-12 Physical Component Summary and Mental Component Summary, in patients ≥ 18 years at consent

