4. PATIENT POPULATION

4.1. Patient Definitions

The populations (analysis sets) are defined as follows:

- Safety Analysis Set: All patients who received any amount of lumasiran during study.
- Full Analysis Set: All patients who received any amount of lumasiran and have at least one evaluable plasma oxalate value (pre-dialysis in Cohort B) at baseline and at least one evaluable plasma oxalate value from assessment(s) at Month 3 through Month 6
- PK Analysis Set: All patients who received any amount of lumasiran, have at least 1 postdose blood sample for PK parameters, and have evaluable PK data.

The Safety Analysis Set will be used for safety analyses and the sensitivity analysis of efficacy. The Full Analysis Set will be used to evaluate efficacy endpoints. The PK Analysis Sets will be used to conduct PK analyses.

This study will consist of 2 periods: a 6-month Primary Analysis Period followed by a long-term (54 months) extension period. The Primary Analysis Period starts at the first date/time of lumasiran dose administration and ends at either the date/time of lumasiran dose administration at Month 6 (exception being that Month 6 assessments (eg, plasma oxalate and PK assessments) which occur after the Month 6 dose will be included) or the date of the Month 6 visit (Day 169) for patients who discontinued treatment prematurely. Primary analysis will be conducted using the Primary Analysis Period data collected through 6 months.

The Long-term Extension Period, starts at the date/time of lumasiran dose administration at Month 6 and is through the end of the study. Analysis of the Long-term Extension Period will focus on long-term efficacy and safety effects of lumasiran.

Patients who discontinue from study drug during the 6-month Primary Analysis Period (defined above) will be encouraged to remain on the study and complete assessments (including plasma oxalate but excluding PK assessments) through Month 6. They will also be asked to complete safety follow-up visits, once every 3 months, per the safety follow-up schedule for up to 12 months after the last dose of lumasiran.

Patients who discontinue study drug after Month 6 will be asked to return for their next scheduled visit to complete early termination (ET) assessments and complete safety follow-up visits, once every 3 months, per the safety follow-up schedule for up to 12 months after the last dose of lumasiran.

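### SAP 5.5 dates partially dated renal stones to the start of the month or year with no floor at the first dose, which can only shift stones out of treated or extension time, usually by a small amount

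*SAP*

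**What the plan says.** Stone frequency is a secondary endpoint, listed in SAP 3.2 under the Long-term Extension Period only ("Frequency of renal stone events"). Partial dates are handled in SAP 5.5: "For partial dates of renal stone events (start and stop dates): the first day/month will be imputed for start date", with stop dates set to the last day or month. The section adds: "It is not expected that renal stone dates will be completely missing". It sets no limit at the first dose or at the Month 6 dose.

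Both periods begin at a dose. SAP 4.1 says "The Primary Analysis Period starts at the first date/time of lumasiran dose administration", and the extension "starts at the date/time of lumasiran dose administration at Month 6 and is through the end of the study". The baseline stone count is the history reported at screening (SAP 5.4, with the age adjustment in SAP 10.1). It is not built from dated on-study events.

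For adverse events, SAP 5.5 assigns no date and resolves doubt towards treatment: "An AE will be considered treatment emergent unless it can be unequivocally determined" from the partial dates that the event came before the first dose. Stones are outside that rule, because Protocol 6.3.2 says: "Since renal stone events are recorded as an efficacy assessment for lumasiran, these will not be treated as AEs or SAEs".

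**The concern.** Suppose a stone occurs shortly after the first dose and only its month is recorded. The rule dates it to the 1st of that month, which is before treatment unless dosing was on the 1st. The screening history need not contain it, so it may be counted nowhere. The same mechanism at the Month 6 dose moves an extension stone into the Primary Analysis Period, for which stone frequency is not a listed endpoint.

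The study has no control group, so the natural reference for the treated stone rate is each patient's own history. An error that can only remove events from the treated side favours the drug. With 20 planned patients, stone counts may be small enough for one misplaced event to show. The wording is the same as the convention for medications in that section. There an early start does little harm, because a drug can be both prior and concomitant. For a counted efficacy event it can change the count.

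**Working it through.** The documents give no stone rate, event count or share of partial dates, so there is no figure of the plan to reproduce. The check asks how much treated time the rule can displace.

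**Inputs from the documents**
- Imputation rule: SAP 5.5.
- Period starts: first dose and Month 6 dose (SAP 4.1).
- A month is 28 days (notes to Protocol Table 1). The primary period is 6 × 28 = 168 days, the extension 54 × 28 = 1512 days, and the total 1680 days.

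**Assumptions**
- The imputed start date assigns the period.
- The stone rate is constant and follow-up is complete.
- The Month 6 dose is on Day 169.
- The first dose is equally likely on each of the 366 dates of one calendar year.
- A share f of stones is partially dated. It is unknown, so 5% to 50% is shown, with 100% as the upper bound.

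**Direction.** With a first dose on 16 March and a stone on 25 March whose day is missing, the imputed start is 1 March, before dosing. An imputed date is never later than the true date, so no pre-dose stone can move into treatment.

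**Displaced time per patient if every stone is partially dated** (mean days over all 366 first-dose dates)

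| Shift | Day missing | Day and month missing |
|---|---|---|
| Primary to pre-dose | 14.8 | 129.2 |
| Extension to pre-dose | 0.0 | 53.3 |
| Extension to primary | 14.7 | 128.8 |

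**Loss = displaced days / period days**
- Primary stones moved before the first dose: 14.8/168 = 8.8% (day missing); 129.2/168 = 76.9% (year only).
- Extension: 14.7/1512 = 1.0%, ratio 0.990; (53.3 + 128.8)/1512 = 12.0%, ratio 0.880.
- All treated time: 14.8/1680 = 0.9%, ratio 0.991; (129.2 + 53.3)/1680 = 10.9%, ratio 0.891.
- Primary period, net of stones arriving from the extension: ratio 1.000 (day missing) and 0.997 (year only), from unrounded values.

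**Scaling to a share f: ratio = 1 − f × loss**

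| Rate | Day missing, f = 5% to 50% | Year only, f = 5% to 50% |
|---|---|---|
| Extension | 0.9995 to 0.995 | 0.994 to 0.940 |
| All treated | 0.9996 to 0.996 | 0.995 to 0.946 |

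**Month 12 data cut** (168 extension days, 336 treated days), every stone partially dated: the extension loses 8.8% (day missing) or 76.9% (year only), and all treated time loses 4.4% or 54.0%.

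**With a floor at the first dose**, the loss there is 0 and the all-treated ratio is 1.000. Placing every ambiguous Month 6 stone in the extension also brings the extension loss to 0, but true primary-period stones from that month or year then count in the extension.

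**The case against.** The strongest objection is that the deciding text cannot be seen. The effect needs the imputed start date to assign the period, and SAP 7.3.4.5 is redacted. Visible text could point elsewhere: SAP 5.2 summarises data collected during each period, and SAP 5.6 tabulates by the visit recorded on the eCRF, though it is unclear whether that covers continuously recorded events. Assignment by visit, or by the imputed stop date, would reduce or remove the effect. This stands, and the redaction itself is not a fault in the plan.

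A reader might infer that the rule lowers the treated stone rate at both boundaries. The documents do not support that. A stone moved out of the extension usually lands in the Primary Analysis Period, which is also on treatment. The extension rate then falls, but the all-treated rate does not.

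A reader might also infer a large bias from the dosing month alone. In a 30-day month with uniform days, 465 of 900 dose-and-event pairs (52%) have the stone on or after the dose, and 435 of those 465 (94%) are imputed before it when the day is missing. Those shares apply only to partially dated stones in that month and are not effects on the endpoint.

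Year-only dates also look unlikely. Stones are recorded continuously, visits are monthly to Month 6 and at least every 3 months afterwards (Protocol 3.1), and Protocol 6.3.2 asks for supporting medical records. Listings would let a reader check events near a boundary.

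Finally, the adverse event rule is only a partial model. It sets a flag at the first dose and is silent on Month 6, so it supports a first-dose floor but not sending every ambiguous stone to the extension.

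**Conclusion.** The point holds in a limited form. The rule has no first-dose floor, its error runs only towards earlier dates, and the adverse event safeguard does not reach stones. If the imputed start date assigns the period, the rule can drop a treated stone from every count and can lower the extension and all-treated rates.

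When only the day is missing, the effect over full follow-up is at most about 1%, even if every stone is affected. It reaches about 9% of extension stones at a Month 12 cut. Losses of 12% or more in the extension need year-only dates for all stones. These are upper ends that scale with the unknown partial share, under a constant stone rate and full follow-up. The direction is certain given the rule; the size is not. The endpoint is secondary and the plasma oxalate primary analysis is untouched. The case for changing the rule rests on its one-way direction and the very low cost of the remedy.

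**What to change.** In SAP 5.5, replace the start-date rule for stones with: impute the earliest date consistent with the known parts of the date, but not before the first lumasiran dose, unless the known parts or the stop date show that the stone began before dosing. State also which date assigns a stone to a period, if the redacted text does not already do so.

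Where a partial date is compatible with both sides of the Month 6 dose, do not force the stone into the extension, since that would over-count there. Report the extension rate under both placements as a sensitivity analysis.

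The cost is a sentence or two in the SAP, a small change to the derivation and one extra display. A truly pre-dose stone with an ambiguous date would now count as treated, so the treated stone rate may be slightly less favourable.
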